### **6.6. Treatment of Overdose**

For this study, any dose of study drug greater than 300 mg within a 24-hour time period will be considered an overdose.

In the event of an overdose, the investigator should:

- Contact the medical monitor immediately
- Evaluate the subject to determine, in consultation with the medical monitor, whether study drug should be interrupted or whether the subsequent study dose should be reduced
- Closely monitor the participant for any AE/SAE and laboratory abnormalities

## 6.7. Concomitant Therapy

Any medication or vaccine (including over-the-counter or prescription medicines, recreational drugs, vitamins, and/or herbal supplements) that the subject is receiving at the time of enrollment or receives during the study must be recorded along with:

- Reason for use
- Dates of administration including start and end dates
- Dosage information including dose and frequency

MLS-101 may alter the clearance of drugs that rely on multidrug and toxin extrusion 1 (MATE1) transport for clearance. While the diabetic medication metformin is transported by MATE1, it can also be cleared by MATE2 and organic cation transporter; thus, significant changes in metformin bioavailability are thought to be unlikely. However, it is prudent to periodically monitor blood glucose levels as per protocol in study subjects taking metformin. Clinically significant changes in glucose control should be considered possibly related to study drug and treated accordingly with laboratory confirmation and appropriate medical interventions deemed appropriate by the site investigator and other treating healthcare providers. The medical monitor should be consulted if discontinuation of study drug is considered.

### 6.7.1. Prohibited Treatments

The following medications are prohibited:

- Concomitant use of epithelial sodium channel inhibitors or mineralocorticoid receptor antagonists, including, but not limited to amiloride, triamterene, spironolactone, eplerenone
- ACE inhibitors and ARBs in combination as background antihypertensive treatment
- Chronically administered oral or topical corticosteroids within 3 months of Screening or during study participation. Short-term (ie,  $\leq$  2 weeks) of topical corticosteroids are allowed if taken  $\geq$  1 month prior to Randomization.
- Sympathomimetic decongestants within 1 week of Screening or during study participation
- Theophylline unless treatment has been stable at optimum dose for at least 4 weeks prior to Screening and remains stable during study participation
- Regular use of phosphodiesterase type 5 inhibitors within 3 months of Screening or during study participation
- Chronic use of NSAIDs, other than low dose aspirin (81-325 mg), where chronic use is defined as  $>$  3 consecutive or nonconsecutive days of treatment per week. Note: intermittent use of NSAIDs is strongly discouraged; if required, NSAIDs must not be taken more than a total of 2 days during the study (defined as the period from Randomization to the end of study period). If analgesics are required, acetaminophen is recommended.
- Intramuscular steroids within 3 months of Screening or during study participation
- Short-acting nitrates taken for angina for underlying cardiac disease. Chronic, long-acting doses of nitrates are acceptable.
- Estrogen- or progesterone-containing oral contraceptives or implantable progesterone devices

- Strong CYP3A and CYP3A4 inhibitors (eg, clarithromycin, telithromycin, nefazodone, itraconazole, ketoconazole, atazanavir, darunavir, indinavir, lopinavir, nelfinavir, ritonavir, saquinavir, tipranavir)
- Strong CYP3A and CYP3A4 inducers (eg, apalutamide, carbamazepine, enzalutamide, fosphenytoin, lumacaftor, mitotane, phenobarbital, phenytoin, primidone, rifampin, St. John's Wort)

The decision to administer a prohibited medication/treatment during the study period is done with the safety of the subject as the primary consideration. When possible, the sponsor is to be notified before the prohibited medication/treatment is administered. If the investigator determines that any of the prohibited treatments listed above are necessary for proper care of the subject during the study, the investigator should recommend a treatment plan in consultation with the medical monitor that will allow the subject to remain in the study.

### **6.7.2. Permitted Treatments**

Background antihypertensive treatment of  $\geq 2$  drugs (note: a combination pill = 2 antihypertensives) that have been stable at their prescribed doses for at least 4 weeks prior to signing the Screening/main study ICF are permitted. Any treatment other than those listed in [Section 6.7.1](#) is allowed and should be documented in the eCRF.

## 7. DISCONTINUATION/WITHDRAWAL CRITERIA

### 7.1. Discontinuation of Study Drug

Subjects who wish to stop treatment for any reason may stop at any time during the study. If the study treatment is permanently discontinued, the subject will remain in the study to complete all assessments as described in the SoA ([Table 1](#) and Table 2) through Study Week 8 (end-of-treatment visit). Subjects should also be encouraged to return for a final follow-up visit 4 weeks after the Study Week 8 visit for Part 1 and 2 weeks after the Study Week 8 visit for Part 2, at which the end-of-study assessments will be performed.

Details regarding subjects who discontinue study drug before Study Week 12 in Part 1 or Study Week 10 in Part 2 will be recorded on the appropriate page(s) of the eCRF. If a subject discontinues study drug because of an AE, the investigator may be requested to schedule follow-up visits until the event has resolved or stabilized ([Section 8.3.3](#)).

Reasons for discontinuing study drug may include:

- Use of prohibited/excluded medications (see [Section 6.7.1](#))
- Administrative decision by the investigator or the sponsor
- Subject noncompliance with the study drug dosing schedule ([Section 6.4](#))
- Development of an AE ([Section 8.3](#))
- Unblinding of subject's study drug treatment assignment ([Section 6.3](#))
- Subject becomes pregnant ([Section 8.3.5](#))
- Other

### 7.2. Discontinuation/Withdrawal of Subjects

Subjects have the right to withdraw participation from the study at any time and for any reason and will be removed from the study upon request. However, the investigator will encourage subjects to return for subsequent observations in order to minimize the number of missing data points. If a subject is unable or unwilling to return, the reason for withdrawal will be recorded. Each subject's right to withdraw will be honored; subjects who desire no further follow-up contact will be asked to declare so in writing. Details regarding subjects who choose to discontinue study participation before Study Week 12 in Part 1 or Study Week 10 in Part 2 will be recorded on the appropriate page(s) of the eCRF.

Reasons for discontinuing/withdrawing from study may include:

- Withdrawal from participation due to subject convenience (ie, due to a change in the subject's willingness or ability to attend study visits, eg, resulting from new job, work schedule change, or move to another geographical area)
- Lost to follow-up (ie the investigator has exhausted all reasonable methods of contacting the subject, which should be documented by at least 3 unsuccessful attempts to contact the subject) ([Section 7.3](#))
- Death
- Other

### **7.3. Lost to Follow Up**

A subject will be considered lost to follow-up if he/she repeatedly fails to return for scheduled visits and is unable to be contacted by the study site.

The following actions must be taken if a subject fails to return to the clinic for a required study visit:

- The site must attempt to contact the subject and reschedule the missed visit as soon as possible, counsel the subject on the importance of maintaining the assigned visit schedule, and ascertain whether the subject wishes to and/or should continue in the study.
- Before a subject is deemed lost to follow-up, the investigator or designee must make every effort to regain contact with the subject (where possible, [3] telephone calls, and if necessary, a certified letter to the subject's last known mailing address or local equivalent methods). These contact attempts should be documented in the subject's medical record.
- Should the subject continue to be unreachable, he/she will be considered to have withdrawn from the study.

## 8. STUDY ASSESSMENTS AND PROCEDURES

**Table 1**, **Table 2**, and **Section 4.8** outline the SoA and study conduct details, respectively, for all subjects and all study periods (Pre-Screening, Screening, Placebo Run-in, Double-blind Treatment, and Follow-up)

- Study procedures and their timing are summarized in the SoA. Protocol waivers or exemptions are not allowed.
- Acute safety concerns should be discussed with the sponsor immediately upon occurrence or awareness to determine if the subject requires dose modification or discontinuation of study drug.
- Adherence to the study design requirements, including those specified in the SoA, is essential and required for study conduct.
- All Screening evaluations must be completed and reviewed to confirm that potential subjects meet all eligibility criteria. The investigator will maintain a Screening log to record details of all subjects screened and to confirm eligibility or record reasons for Screening failure, as applicable.
- Procedures conducted as part of the subject's routine clinical management (eg, blood count) and obtained before signing of the Screening/main study ICF may be utilized for Screening or baseline purposes provided the procedures met the protocol-specified criteria and were performed within the timeframe defined in the SoA.
- Safety results that could unblind the study will not be reported to investigative sites or other blinded personnel until the study has been unblinded.

### 8.1. Efficacy Assessments

#### 8.1.1. Automated Office-Measured Blood Pressure

Accurate measurement of BP is essential to classify individuals and record study treatment effect; consequently, BP should be measured by an automatic BP device at the site that is identical for all participating sites and managed by qualified personnel. In addition, the same person should use the BP device for a given subject at each visit whenever possible, and the measurement should be performed using the same arm of the subject and the appropriate cuff size, as determined during the pre-Screening visit.

The BP must be measured at trough (ie, before study drug administration) and at approximately the same time of day (preferably between 7:00 and 10:00 am  $\pm 1$  hour). The subject should be relaxed, sitting in a chair (feet on floor, back supported) for  $> 5$  minutes. The subject should avoid caffeine, exercise, and smoking for at least 30 min before measurement, and ensure patient has emptied his/her bladder. Neither the subject nor the observer should talk during the rest period or during the measurement. Remove all clothing covering the location of cuff placement.

Details on BP procedure (measurement and transfer of data) including subject preparation (eg, arm selection, arm position, cuff size) will be provided in the BP manual and will follow the AHA guidelines.

At each timepoint indicated in the SoA, SBP and DBP will be measured 5 times using an automated oscillometric sphygmomanometer device provided by the sponsor after approximately 5 minutes of rest in the seated position according to the AHA Guidelines ([Muntner 2019](#)); the repeated measurements should be separated by 1 to 2 minutes. The last 2 of 5 unattended

measurements of SBP and DBP will be averaged for the analysis. In addition to sitting measurements, standing BP will be measured at Screening/start of Placebo Run-in, Randomization, Study Week 1, and Study Week 8 with the AOBP device to assess for hypotension according to the procedure provided in [Appendix 12.5](#).

### **8.1.2. 24-hour Ambulatory Blood Pressure Monitoring**

Subjects will be monitored by ABPM for 24 hours before the first dose on Study Day 1 and before the first dose on Study Day  $49 \pm 2$  days (end of Week 7) according to the method described in the AHA scientific statement on measuring BP in humans ([Muntner 2019](#)). Blood pressure will be measured automatically every 15 to 30 minutes for a 24-hour period using an ABPM device provided to each site by the central BP laboratory or the sponsor for the duration of the study. The ABPM data will be electronically transferred to the central BP laboratory and subsequently to the contract research organization. Details on ABPM procedure (installation, recording, and transfer of data), including subject preparation, will be provided in the BP manual. At the second clinic visit of the Placebo Run-in period (Visit 4), subjects will be given an ABPM device and instructions by the investigator on how to perform the ABPM procedure at home. Subjects will participate in a telephone visit on Study Day 0 (Visit 5) in which they will be reminded of the instructions on how to perform the ABPM procedure at home by the investigator or study coordinator. The ABPM procedure will be initiated at home approximately 24 hours before Randomization (Study Day 1) and again in the clinic at the end of Study Week 4 (ie, Visit 10, Study Day  $28 \pm 2$ ) in Part 2 and Study Week 7 (ie, Visit 13; Study Day  $49 \pm 2$ ) in Parts 1 and 2. Alternatively, sites may choose to schedule an office visit on Study Day 0 (Visit 5) to initiate the ABPM procedure (the ABPM procedure will be initiated in the clinic at Study Weeks 4 and 7 unless a subject is not able to attend the visit due to extraordinary circumstances, such as COVID-19 restrictions including site closure, subject exposure to COVID-19, or subject testing positive for COVID-19). If, for any reason, the ABPM procedure is deemed a failure at the end of Study Week 7, it can be repeated at Study Week 8. Training for the ABPM procedure can be done at an office visit or via phone.

## **8.2. Safety Assessments**

### **8.2.1. Medical History**

Medical history data are to be collected at the time of Pre-Screening and updated at the time of Screening.

### **8.2.2. Physical Examination**

A complete physical examination, including height and weight, will be carried out by trained medical personnel at Screening/start of Placebo Run-in, Randomization, and at Study Week 8 (end of treatment).

### **8.2.3. Vital Signs**

Vital signs including body temperature, heart rate, and respiratory rate are to be recorded at each study visit throughout the study. All measurements will be assessed with the subject in a seated position. Subjects should be seated for at least 5 minutes before taking the measurement. Pulse should be measured in the brachial/radial artery for at least 15 seconds.

#### **8.2.4. Electrocardiogram**

Single 12-lead ECGs will be recorded at Screening/start of Placebo Run-in, Randomization (Baseline), and at the Study Week 8 (end-of-treatment) visit. Parameters to be recorded include PR, QRS, and QT intervals, and corrected QT interval using Fridericia's formula.

Measurements will be taken after the subject has rested for at least 10 minutes in a supine position using a 12-lead (I, II, III, aVR, aVL, aVF, V1-V6) ECG system over a duration of 10 seconds. The chart speed will be set at 25 mm/sec. ECG changes consistent with hyperkalemia will require confirmation of potassium levels at a local laboratory.

#### **8.2.5. Clinical Safety Laboratory Tests**

Clinical safety laboratory tests will be conducted by a central laboratory according to the time points specified in [Table 1](#) and Table 2. Instructions for collection, preparation, handling, and shipping clinical laboratory specimens are provided in the Laboratory Manual for the study. Analytes for clinical safety labs are listed in [Table 6 \(Appendix 12.9\)](#).

#### **8.2.6. Spot Urine and 24-Hour Urine Collection**

Subjects will be given either a spot urine collection kit for Part 1 or a 24-hour urine collection kit for Part 2 on the second visit of the placebo-run in period (Visit 4) to take home for use on Study Day 1. In Part 1 of the study, first morning urine will be collected prior to morning dose of study drug on Study Day 1 and again at the end of Study Week 8 (ie, Study Day  $56 \pm 2$  or end-of-treatment period) for determination of potassium, sodium, and creatinine levels. In Part 2 of the study, 24-hour urine will be collected on Study Day 1 and again at the end of Study Week 4 (ie, Visit 10, Study Day  $28 \pm 2$ ) for determination of potassium, sodium, creatinine, and aldosterone levels.

#### **8.2.7. Pregnancy Testing**

Pregnancy tests will be performed as shown in [Table 1](#) and Table 2. A serum pregnancy test will be performed at Screening/start of Placebo Run-in, and urine pregnancy tests will be performed at Randomization (Study Day 1) and at the Study Week 4 and Study Week 8 (end-of-treatment) visits. Pregnancy tests are required for women of childbearing potential only. Note that a woman is considered to be of childbearing potential, ie, fertile, following menarche and until becoming postmenopausal unless permanently sterile. Permanent sterilization methods include hysterectomy, bilateral salpingectomy, and bilateral oophorectomy. A postmenopausal state is defined as no menses for 12 months without an alternative medical cause. A high follicle stimulating hormone level in the postmenopausal range must be used to confirm postmenopausal status in all postmenopausal women at Screening/start of Placebo Run-in.

### **8.3. Adverse Events, Serious Adverse Events, and Other Safety Reporting**

The definitions of AEs and SAEs are provided in [Appendix 12.10](#). Adverse events will be reported by the subject. The investigator and any qualified designees are responsible for detecting, documenting, and recording events that meet the definition of an AE or SAE, and remain responsible for following up on all AEs and SAEs. The method of recording, evaluating, and assessing causality of AEs and SAEs, as well as the procedures for completing and transmitting safety event report forms are provided in [Appendix 12.10](#).

### **8.3.1. Time Period and Frequency for Collecting AE and SAE Information**

All AEs and SAEs will be collected from Screening/start of Placebo Run-in (after signed Screening/main study ICF) until 30 days post last dose of study drug in Part 1 (Study Week 12) and 15 days post last dose of study drug in Part 2 (Study Week 10) at the timepoints specified in the SoA ([Table 1](#) and Table 2).

Adverse events that begin before the start of study drug, but after obtaining informed consent will not be considered treatment-emergent AEs. Adverse events collected during Placebo Run-in are considered treatment-emergent events.

All SAEs occurring from Screening/start of Placebo Run-in (after signed Screening/main study ICF) until 30 days post last dose of study drug in Part 1 (Study Week 12) and 15 days post last dose of study drug in Part 2 (Study Week 10) will be recorded and reported to the sponsor or designee immediately and under no circumstance should this exceed 24 hours. The investigator will submit any updated SAE data to the sponsor within 24 hours of it being available.

Investigators are not obligated to actively seek information on AEs or SAEs after conclusion of the study participation. However, if the investigator learns of any SAE, including a death, at any time after a subject has been discharged from the study, and he/she considers the event to be reasonably related to the study drug or study participation, the investigator must promptly notify the sponsor.

In the event that study drug is interrupted, AEs and SAEs will be collected throughout the interruption. If study drug is discontinued for any reason, the reason will be recorded and the subject should be encouraged to remain in the study so that important safety information can be obtained. All AEs and SAEs leading to discontinuation of study drug or discontinuation of study will be collected. Once a subject withdraws consent to participate in the study, no further information can be collected from the subject.

### **8.3.2. Method of Detecting AEs and SAEs**

Care will be taken not to introduce bias when detecting AEs and/or SAEs. Open-ended and nonleading verbal questioning of the subject is the preferred method to inquire about AE occurrences.

Investigators will seek information on AEs at each subject contact. All AEs, whether reported by the subject or noted by study personnel, will be recorded in the subject's medical record and on the AE eCRF.

A consistent, nondirective questioning methodology should be adopted for eliciting AE information at all subject evaluation timepoints. Examples of nondirective questions include the following:

- “How have you felt since your last clinic visit?”
- “Have you had any new or changed health problems since you were last here?”

The method of recording, evaluating, and assessing causality of AEs and SAEs, and the procedures for completing and transmitting SAE reports are provided in [Appendix 12.10](#).

### **8.3.3. Follow-up of AEs and SAEs**

After the initial AE/SAE report, the investigator is required to proactively follow each subject at subsequent visits/contacts. All SAEs and AEs of special interest (as defined in [Section 8.3.7](#)) will be followed until resolution, stabilization, the event is otherwise explained, or the subject is lost to follow-up (as defined in [Section 7.3](#)).

### **8.3.4. Regulatory Reporting Requirements for SAEs**

- Prompt notification (within 24 hours) by the investigator to the sponsor/designee of an SAE is essential so that legal obligations and ethical responsibilities towards the safety of subject and the safety of a study intervention under clinical investigation are met.
- The sponsor has a legal responsibility to notify both the local regulatory authority and other regulatory agencies about the safety of a study intervention under clinical investigation. The sponsor will comply with country-specific regulatory requirements relating to safety reporting to the regulatory authority, IRBs/IECs, and investigators.
- An investigator who receives an investigator safety report describing an SAE or other specific safety information (eg, summary or listing of SAEs) from the sponsor will review and then file it along with the Investigator Brochure and will notify the IRB/IEC, if appropriate according to local requirements.
- Investigator safety reports must be prepared for suspected unexpected serious adverse reactions according to local regulatory requirements and sponsor policy and forwarded to investigators as necessary.
- Any life-threatening (ie, imminent risk of death) or fatal AE that occurs while on study drug should be submitted to the medical monitor/designee with written case details on a safety event report form within 24 hours.

### **8.3.5. Pregnancy**

- Details of all pregnancies in female subjects and female partners of male subjects will be collected after the start of the Placebo Run-in and until 30 days (Part 1) and 15 days (Part 2) after the last subject visit.
- If a pregnancy is reported, the investigator will record pregnancy information on the appropriate form and submit it to the sponsor within 24 hours of learning of the female subject or female partner of male subject (after obtaining the necessary signed informed consent from the female partner) pregnancy.
- While pregnancy itself is not considered to be an AE or SAE, any pregnancy complication or elective termination of a pregnancy for medical reasons will be reported as an AE or SAE.
- Abnormal pregnancy outcomes (eg, spontaneous abortion, fetal death, stillbirth, congenital anomalies, ectopic pregnancy) are considered SAEs and will be reported as such.
- The subject/pregnant female partner will be followed to determine the outcome of the pregnancy. The investigator will collect follow-up information on the subject/pregnant female partner and the neonate and the information will be forwarded to the sponsor/designee.
- Any poststudy pregnancy-related SAE considered reasonably related to the study drug by the investigator will be reported to the sponsor as described in [Section 8.3.4](#). While the investigator is not obligated to actively seek this information in former study

subject/pregnant female partner, he or she may learn of an SAE through spontaneous reporting.

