#### **4.8.14. Telephone Visit (Visit 15, BP check; Study Day 59 + 2 Days)**

Subjects will complete a BP check approximately 3 days post last dose of study drug. On Study Day  $59 \pm 2$  days, subjects will participate in a telephone visit during which they will perform the following procedure at home:

- BP check

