#### **4.8.15. Study Week 10 (Part 2 Only: Visit 16, End of Study; Study Day 70 $\pm 3$ Days)**

On Study Day  $70 \pm 3$  days, subjects will return to the site for an end-of-study visit scheduled 2 weeks after the last treatment with study drug and the following procedures will be performed:

- Vital signs (body temperature, heart rate, respiratory rate)
- AOBP (average of the last 2 of 5 unattended measurements using an automated oscillometric sphygmomanometer device after approximately 5 minutes of rest in the seated position)
- Blood draw ([Table 6](#))
  - Blood samples for aldosterone, cortisol, 11-deoxycorticosterone, 11-deoxycortisol, and PRA will be collected
  - Blood samples for hematology, chemistry, and coags will be collected, including hemoglobin A1c concentration and ACTH
- Urine will be collected for urinalysis ([Table 6](#))
- Review of AEs and concomitant medications

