#### **4.8.16. Study Week 12 (Part 1 Only: Visit 16, End of Study; Study Day 84 $\pm 3$ Days)**

On Study Day  $84 \pm 3$  days, subjects will return to the site for an end-of-study visit scheduled 4 weeks after the last treatment with study drug and the following procedures will be performed:

- Vital signs (body temperature, heart rate, respiratory rate)
- AOBP (average of the last 2 of 5 unattended measurements using an automated oscillometric sphygmomanometer device after approximately 5 minutes of rest in the seated position)
- Blood draw ([Table 6](#))
  - Blood samples for aldosterone, cortisol, 11-deoxycorticosterone, 11-deoxycortisol, and PRA will be collected
  - Blood samples for hematology, chemistry, and coags will be collected, including hemoglobin A1c concentration and ACTH

- Urine will be collected for urinalysis ([Table 6](#))
- Review of AEs and concomitant medications

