## 5. STUDY POPULATION

### 5.1. Inclusion Criteria

1. Male and nonpregnant, nonlactating female subjects  $\geq$  18 years of age. Fertile male and female subjects and their partners must agree to use either highly effective or acceptable methods of contraception as defined in [Appendix 12.8](#) from Screening to 90 days post last dose of study drug
2. Written informed consent Health Insurance Portability and Accountability Act authorization, and local patient privacy required documentation for this study have been obtained
3. Average of AOBP measurements taken at Screening/start of the Placebo Run-in Visit and Randomization with SBP  $\geq$  130 mmHg
4. Background antihypertensive treatment of  $\geq$  2 drugs (note: a combination pill = 2 antihypertensives) that have been stable at their prescribed doses for at least 4 weeks prior to signing the Screening/main study ICF
5. For Part 1, inclusion based on morning pre-Screening visit measurement of PRA, and the value for PRA must be  $\leq$  1 ng/mL/h. For Part 2, inclusion based on morning pre-Screening visit measurement of PRA, and the value of PRA must be  $>$  1 ng/mL/h. Alternative target PRA criteria for the study may be provided by the sponsor. These alternative targets may be adjusted during the conduct of the trial based on ongoing review of PRA values.
6. Inclusion based on morning pre-Screening visit measurement of serum aldosterone for Part 1 and pre-Screening visit measurement of aldosterone for Part 2. The value for aldosterone must be  $\geq$  1 ng/dL based on morning measurement. Alternative target aldosterone criteria for the study may be provided by the sponsor. These alternative targets may be adjusted during the conduct of the trial based on ongoing review of serum aldosterone values.
7. Serum cortisol  $\geq$  18 mcg/dL (morning measurement) or serum cortisol  $>$  3 and  $<$  18 mcg/dL (morning measurement) at Screening/start of Placebo Run-in visit if there is no evidence of adrenal insufficiency based on normal ACTH stimulation test results. In the event that ACTH stimulation testing cannot be performed due to logistical challenges, including supply chain limitations to availability of synthetic ACTH, then subjects may be entered into the trial if morning serum cortisol is  $>$  3 mcg/dL and they fulfill the criteria for no recent use of exogenous corticosteroid medications in dosages that could potentially cause adrenal suppression (ie, Exclusion Criteria 16a).

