### 12.8.2. Contraception Guidance

Investigators should counsel WOCBP and male subjects who are sexually active with WOCBP on the importance of pregnancy prevention and the implications of an unexpected pregnancy. Investigators shall advise these subjects on the use of adequate methods of contraception and will check for adherence during study visits. Subjects must agree to use adequate contraception during the study and for 90 days after the last dose of study drug.

The following methods of contraception are considered adequate for this study:

- **Highly effective methods of contraception** (Table 4): Highly effective methods of contraception have a failure rate of < 1% per year when used consistently and correctly.
- **Acceptable methods of contraception** (Table 5): Acceptable methods of contraception which may not be considered as highly effective have a failure rate of > 1% per year when used consistently and correctly.

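### Required pregnancy collection stops about 58 days (Part 1) and 29 days (Part 2) after last dose, short of the 90 days for which the protocol requires contraception

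*Protocol*

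**What the plan says.** **Collection.** Protocol Section 8.3.5 sets scope and start: "Details of all pregnancies in female subjects and female partners of male subjects will be collected after the start of the Placebo Run-in". It sets the end at "until 30 days (Part 1) and 15 days (Part 2) after the last subject visit". A reported pregnancy is followed to its outcome.

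**Contraception.** Inclusion criterion 1 (Section 5.1) makes fertile subjects and their partners agree to contraception "from Screening to 90 days post last dose of study drug". Appendix 12.8.2 repeats the period: "Subjects must agree to use adequate contraception during the study and for 90 days after the last dose of study drug". Neither distinguishes Part 1 from Part 2.

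**Visit timing.** Part 1 closes with an "end-of-study visit scheduled 4 weeks after the last treatment with study drug" (Section 4.8.16, Day 84 ± 3). Part 2 closes with an "end-of-study visit scheduled 2 weeks after the last treatment with study drug" (Section 4.8.15, Day 70 ± 3). Section 4.8.14 places the Day 59 call relative to the end of dosing: "Subjects will complete a BP check approximately 3 days post last dose of study drug".

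**Testing.** After the serum test at Screening, "urine pregnancy tests will be performed at Randomization (Study Day 1) and at the Study Week 4 and Study Week 8 (end-of-treatment) visits" (Section 8.2.7). Neither end-of-study visit includes a test.

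**After the windows close.** Under Sections 8.3.1 and 8.3.5, a later SAE, including a pregnancy-related one, is reportable if the investigator learns of it and considers it reasonably related to study drug. The investigator has no duty to look for such events.

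**The concern.** The contraception requirement and the pregnancy-collection rule concern the same people after the same last dose, but they end at different times, and the protocol does not say why. Collection stops first in both Parts, and much earlier in Part 2.

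At stake is the completeness of a small body of safety information. An uncomplicated pregnancy in the later part of the 90 days, or one with an abnormal outcome not attributed to study drug, would have no required route to the sponsor. If it is not collected, the follow-up to outcome in Section 8.3.5 does not start. With no scheduled test after Week 8, detection after that visit already depends on subjects coming forward.

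Such pregnancies are possible. Oral hormonal contraceptives and implantable progesterone devices are excluded (exclusion criterion 16g). The permitted methods include a condom alone (Table 5), in a class for which Appendix 12.8.2 gives a failure rate above 1% per year.

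**Working it through.** **Inputs**
- Last dose: about Day 56 (8 weeks of dosing from Day 1; Week 8 visit at Day 56 ± 2, Section 4.8.13).
- Last visit: Day 84 ± 3 in Part 1, Day 70 ± 3 in Part 2.
- Added collection after the last visit: 30 days in Part 1, 15 days in Part 2 (Section 8.3.5).
- Contraception period: 90 days after last dose, both Parts.

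**Step 1. Reproduce the plan's own interval from last dose to last visit**
- Part 1: 84 − 56 = 28 days, the stated 4 weeks.
- Part 2: 70 − 56 = 14 days, the stated 2 weeks.

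**Step 2. End of collection, in days after last dose**

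Formula: (last visit − last dose) + added days.
- Part 1: 28 + 30 = 58. With visit windows, (81 − 58) + 30 = 53 to (87 − 54) + 30 = 63.
- Part 2: 14 + 15 = 29. With visit windows, (67 − 58) + 15 = 24 to (73 − 54) + 15 = 34.

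**Step 3. Days of the 90 without required collection**
- Part 1: 90 − 58 = 32 (range 27 to 37), or 32/90 = 36%.
- Part 2: 90 − 29 = 61 (range 56 to 66), or 61/90 = 68%.

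**Step 4. Compare the Parts.** 29/58 = 0.5. Part 2 has half the post-dose coverage of Part 1. Both the earlier final visit and the shorter addition contribute.

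**Step 5. Subjects who leave the nominal schedule**
- A Part 1 subject who stops drug by Day 24 and still attends at Day 84 is covered for the full period: 84 + 30 − 24 = 90.
- The same sum for Part 2 gives 70 + 15 − 90 = −5, a day before dosing starts. No Part 2 subject seen at Day 70 is covered for 90 days.
- A subject whose last visit coincides with the last dose has only 30 or 15 days of coverage, leaving 60 or 75 days.

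**Step 6. The other reading of *last subject visit*.** Section 4.6 defines the end of study by the last participant's last visit. If Section 8.3.5 means that visit, a subject is fully covered when it falls at least 90 − 30 = 60 days (Part 1) or 90 − 15 = 75 days (Part 2) after that subject's last dose. Early enrollees would meet this. The last subjects to finish would keep the gaps in Step 3.

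**The case against.** The strongest reply is that nothing here is contradictory. Using contraception and reporting pregnancies are separate obligations, a site can meet both as written, and no section says they must end together. That is correct. The point is an unexplained mismatch, not two rules that cannot both be followed.

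Four stronger readings are tempting, and the documents do not support them.
- **Nothing in the tail would be reported.** Section 8.3.5 classes abnormal pregnancy outcomes as SAEs, and a later SAE that the investigator learns of and attributes to study drug must still be reported. What is left out is narrower: pregnancies with a normal outcome or an outcome not so attributed. Routine SAE collection does not fill this, because it ends 30 or 15 days after last dose (Section 8.3.1), before pregnancy collection does.
- **These would be drug-exposed pregnancies.** The two documents give no half-life, the tablet is immediate release (Section 6.1.1), and Section 4.5 describes about 14 hours of enzyme inhibition at 100 mg QD. Exposure a month or two after the last dose is not shown. The only benchmark is the protocol's own 90 days.
- **Part 2 has a higher dose and less follow-up.** Part 1 also has a 100 mg QD arm. The shorter Part 2 addition goes with its shorter follow-up and its 15-day AE window. What stands is that one regimen, under one contraception rule, gets different pregnancy coverage in the two Parts.
- **The shortfall is 60 and 75 days.** Subtracting 30 and 15 from 90 overlooks that collection runs from the last visit. Those figures apply only to a subject whose last visit coincides with the last dose.

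It is also fair to say that the consequence is small. Part 2 plans about 36 subjects, the number of childbearing potential is not given, pregnancy is not a study endpoint, and the SAP only lists pregnancy test results (Section 6.7.2). The consent form is not among the documents, so subjects may already be asked to report later pregnancies.

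**Conclusion.** The mismatch is real and minor. For a subject who completes treatment, about a third of the contraception period in Part 1 and about two thirds in Part 2 carry no required pregnancy collection, and no section extends it. This rests on reading *last subject visit* as each subject's own, on a last dose at about Day 56, and on visits within their windows. Under the other reading, the gap shrinks to the last subjects to finish. It has no bearing on the efficacy analyses, and no number of missed pregnancies can be estimated from the documents. It is worth correcting because the correction is cheap and the information would otherwise have no assured route to the sponsor.

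**What to change.** Reconcile Section 8.3.5 with inclusion criterion 1 and Appendix 12.8.2 so that the pregnancy-collection period and the stated contraception period, both counted from last dose, agree in Part 1 and Part 2. The common length is for the sponsor to settle. If 90 days is kept, collection would have to run about 90 − 28 = 62 days past the last visit in Part 1 (now 30) and 90 − 14 = 76 days in Part 2 (now 15). Counting directly from last dose avoids that conversion and also covers early stoppers. Late pregnancies can be taken as subject-initiated reports. Define *last subject visit* wherever the term remains.

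The cost is revised protocol and consent wording and a longer period in which sites must accept passive reports. No visit, sample or analysis is added.
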